2.1 Open-label Active Surveillance Phase

Participants will enter the open-label active phase on the day that the participant received the open-label vaccination, received a vaccine outside of the study, or is unblinded until the day that the participant consented to Protocol Amendment 7 or the site stops the electronic clinical outcome assessment (eCOA) (whichever comes first).

The open-label phase will include 3 main study cohorts, based on the vaccination schedules received during the open-label phase:

- **Two-dose schedule cohort:** participants who received the 2 doses of the Ad26.COV2.S vaccine according to initial design of the study on Day 1 and Day 57 (Visit 1 and Visit 4), regardless whether this was before or after unblinding.

- **One-dose schedule cohort:** participants who received a single dose of the Ad26.COV2.S vaccine in the context of the open-label vaccination (eg, placebo participants receiving Ad26COV2.S vaccine during cross-over vaccination) or participants who only received one dose of Ad26COV2.S vaccine during the double-blind phase of the study. These participants remain in this cohort until they receive the booster vaccination in the context of Protocol Amendment 6. Participants who will not receive a booster dose will continue in this cohort.
- **Booster dose schedule cohort:** participants who, during the course of the study, have received only a single dose of the Ad26.COV2.S vaccine and received a booster vaccination under Amendment 6, preferably within 6 to 12 months after the initial vaccination, with a minimum of 3 months after the initial vaccination with Ad26.COV2.S.

Data from participants who received a COVID-19 vaccination outside of the study will be described separately (other dose cohort).

The main objective of the open-label active phase of the study is to describe COVID-19 outcomes, safety, and immunogenicity in the different study cohorts. All analyses are descriptive, efficacy evaluations may be done if feasible, ie, if pre-specified criteria are met, as described in the SAP. Up to the implementation of Protocol Amendment 7, (suspected) COVID-19 cases are monitored through active surveillance (see Section 1.3.6.2).

The list of objectives and endpoints of the open-label active surveillance phase are defined below.

Objectives	Endpoints
Secondary	

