Participants from the Ad26.COV2.S arm enrolled during the double-blind phase will continue in the same arm to receive their second dose, if applicable.

Newly enrolled participants in the open-label phase under Amendment 4 will be randomized in a 1:1 ratio to receive either 1 dose or 2 doses of Ad26.COV2.S vaccine. After the study pause, the unblinding visit was scheduled as soon as reasonably practicable and preferably no later than 2 months following local approvals of Protocol Amendment 5 were received.

As of implementation of Protocol Amendment 6, all ongoing eligible participants who received only a single vaccination with Ad26.COV2.S in the study will be offered a single booster dose of Ad26.COV2.S vaccine (5×10^{10} vp) (see table below). Participants who already received 2 vaccinations with Ad26.COV2.S at the 5×10^{10} vp dose level or any COVID-19 vaccinations outside of the study (including the Janssen vaccine) at the time of local approval of Protocol Amendment 6 are not eligible to receive a booster vaccination with Ad26.COV2.S. The booster vaccination will be administered in the open-label phase of the study, preferably within 6 to 12 months after the participant's first Ad26.COV2.S vaccination in the study. If this is not possible, the booster vaccination should not occur earlier than 3 months after the participant's first Ad26.COV2.S vaccination. The Booster Vaccination Visit should preferably coincide with the participant's next scheduled visit (ie, Visit 7 or Visit 8 for the majority of participants) from the original Schedule of Activities (SoA). If not operationally feasible to coincide with an existing visit, an unscheduled visit may be planned. After the booster vaccination visit, participants will continue procedures and visits as in the original SoA. All participants (whether they consent to the booster vaccination or not) will be encouraged to remain in the study and will be monitored for safety, immunogenicity, and efficacy according to their original schedule.

With Amendment 7, active follow-up of suspected COVID-19 will be replaced by passive surveillance (ie, follow-up phone call visits by the site instead of on-site study visits to document new COVID-19 events as [S]AEs and MAAEs) and to record concomitant therapies associated with COVID-19, if available. During these calls, the protocol required safety information (eg, [S]AEs, AESIs, MAAEs 6 months after the last vaccination) are also collected.

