Stage 1: the study will start by enrolling approximately 1,000 participants in 2 age-dependent subgroups (≥ 18 years to < 60 years of age and ≥ 60 years of age) without comorbidities that are associated with increased risk of progression to severe COVID-19 (including approximately 500 Ad26.COV2.S recipients and approximately 500 placebo recipients), then vaccination will be paused to allow the Independent Data Monitoring Committee (IDMC) to examine Day 3 safety data (ie, from Day 1 to Day 3; including safety data from the ongoing studies).

Stage 2: if no safety concerns are identified in Stage 1, enrollment will proceed, expanding enrollment to participants with or without comorbidities that are associated with increased risk of progression to severe COVID-19 in 2 age-dependent subgroups (≥ 18 years to < 60 years of age and ≥ 60 years of age) (see Section 1.2 [Figure 1] for a schematic overview of the study and Section 5.2 for the list of relevant comorbidities).

Following Ad26.COV2.S EUA in the US and approval of Protocol amendment 4 by both Health authority and IEC/IRB, a single dose of Ad26.COV2.S will be offered to enrolled participants who initially received placebo, resulting in de facto unblinding of participants and investigators. Prior to the unblinding visit, participants may be unblinded upon their request to receive a different authorized/licensed COVID-19 vaccine. Since the study is expected to still be enrolling at the time of EUA, participants who received 1 dose or 2 doses of placebo will receive a single dose of Ad26.COV2.S as their next dose, and participants yet to be enrolled will be randomized (1:1) to either a single-dose or a 2-dose schedule of Ad26.COV2.S. Participants from the Ad26.COV2.S arm will receive the second vaccination, if applicable (Section 6.4). All participants will be encouraged to remain in the study and will be followed for efficacy, safety, and immunogenicity, as originally planned. This will allow assessment of the level of efficacy and duration of protection of a 2-dose schedule of Ad26.COV2.S compared to the single-dose schedule, as well as a direct

comparison of the immunogenicity of the 2 schedules, whereby the single dose is introduced at different time points.

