Participants who have become infected with SARS-CoV-2 may receive a single dose of Ad26.COV2.S vaccine if they have recovered from the acute illness and at least 1 month has passed since recovery, based on the investigator's judgement, and after being made aware that the safety and efficacy data on vaccinating a previously infected individual is limited. These participants will follow the Schedule of Activities from Section 1.3.4 and will resume Schedule of Activities 0 afterwards.

Participants eligible to receive a single dose of Ad26.COV2.S will follow the procedures detailed in Section 8.8 and the Schedule of Activities (Section 1.3.4) and will resume the Schedule of Activities from Section 1.3.3.

Participants from the Ad26.COV2.S arm enrolled during the double-blind phase:

Depending on the participant status at time of unblinding visit, participants may or may not have received their second dose:

- Those who had already received their 2 doses at time of unblinding visit will follow the Schedule of Activities from Section 1.3.4 for unblinding visit and will resume Schedule of Activities from Section 1.3.3 afterwards but will not be vaccinated.
- If the participant has not yet received the second dose at the time of the unblinding visit, the second dose will be administered as planned, at Visit 4 (Day 57) (Schedule of Activities 1.3.3)
- Participants who met vaccination discontinuation rules between vaccination 1 and vaccination 2 applicable during the double-blind phase (Section 7.1) will not receive a second dose of Ad26.COV2.S except participants who have become infected with SARS-CoV-2 who may receive their second dose of Ad26.COV2.S vaccine if they have recovered from the acute illness and at least 1 month has passed since recovery, based on the investigator's judgement. They will also have to be made aware that the safety and efficacy data on vaccinating a previously infected individual is limited. These participants will follow the Schedule of Activities from Section 1.3.4 (at which the vaccination 2 may occur) and will resume Schedule of Activities from Section 1.3.3 afterwards).

Participants initially enrolled in the Ad26.COV2.S group during the double-blind phase who are not eligible to receive a second vaccination will be assured they received the dose level that was submitted for EUA or conditional approval (single-dose schedule of 5×10^{10} vp Ad26.COV2.S).

Participants newly enrolled in the study (under Amendment 4)

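### The open-label cohorts are formed by doses received, and no stated objective compares the participants randomised under Amendment 4 to one versus two active doses by assigned schedule

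*Protocol*

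**What the plan says.** The Synopsis and Section 3, both under 2.1 Open-label Active Surveillance Phase, form three main cohorts "based on the vaccination schedules received during the open-label phase".

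- **Two-dose cohort:** anyone given active vaccine on Day 1 and Day 57, "regardless whether this was before or after unblinding".
- **One-dose cohort:** "participants who received a single dose of the Ad26.COV2.S vaccine in the context of the open-label vaccination", with placebo cross-overs as the example, or "participants who only received one dose of Ad26COV2.S vaccine during the double-blind phase of the study". Members leave it when boosted under Amendment 6.
- **Booster cohort:** single-dose recipients once boosted. Recipients of outside COVID-19 vaccines are described separately.

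The Synopsis (Overall Design) and Section 4.1 say that people newly enrolled under Amendment 4 "will be randomized in a 1:1 ratio to receive either 1 dose or 2 doses of Ad26.COV2.S vaccine". Section 6.4 repeats this. Under Section 6.3, IWRS still assigns these people to vaccine or placebo, and those assigned placebo instead get one active dose on Day 1.

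Section 2.1 (Study Rationale), having said that everyone will be encouraged to stay and be followed, continues: "This will allow assessment of the level of efficacy and duration of protection of a 2-dose schedule of Ad26.COV2.S compared to the single-dose schedule". The same sentence adds a direct immunogenicity comparison of the two schedules, with the single dose starting at different times.

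The open-label objectives in the Synopsis and Section 3 describe COVID-19 outcomes, safety and immunogenicity by cohort. They are declared descriptive, with efficacy evaluated only if feasible.

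**The concern.** The protocol creates a randomised one- versus two-dose contrast and tells the reader that schedules will be compared, but it then sets up reporting groups that do not keep the randomised arms apart. Readers will naturally set the one-dose cohort's incidence beside the two-dose cohort's and take the difference as the effect of the second dose. That difference would also reflect when people were dosed, which variants then circulated, how long ago the last dose was, and why some had only one dose. Section 2.1 itself says that protection differs by variant, so calendar time matters here. Among the newly enrolled, randomisation balances calendar time and prior infection at baseline.

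**Working it through.** The question is about design, and the protocol gives no figure for it. Its one sizing statement (104 events, about 90% power) concerns the double-blind hypothesis. The check therefore sets the definitions side by side.

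**Step 1. Who enters each cohort**

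| Origin | Cohort | Active dosing | How the number of doses was settled |
|---|---|---|---|
| Original active arm, both doses | Two-dose | Day 1 and Day 57, before or across unblinding | Randomised against placebo, then received dose 2 |
| Original active arm, no dose 2 | One-dose | Day 1 in the double-blind phase | Post-randomisation events |
| Placebo cross-over | One-dose | At the unblinding visit, later in the epidemic | Accepted the offer |
| Newly enrolled, assigned two doses | Two-dose, if both given | Day 1 and Day 57, after Amendment 4 | Randomised 1:1 |
| Newly enrolled, assigned one dose | One-dose (inferred) | Day 1, after Amendment 4 | Randomised 1:1 |

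The last row is an inference. The one-dose definition does not name these participants, but its example wording leaves room for them. On a narrower reading, in which open-label vaccination means only the placebo cross-over dose, they belong to no cohort. Neither reading keeps the two randomised arms together as a comparison.

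**Step 2. What a cohort contrast mixes**

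- *Calendar time, variant and time since dose.* Cross-overs received their first active dose at unblinding. Original active-arm participants began earlier.
- *Selection.* Section 6.4 says of the original active arm: "Participants who met vaccination discontinuation rules between vaccination 1 and vaccination 2 applicable during the double-blind phase (Section 7.1) will not receive a second dose". The sentence goes on to except participants infected with SARS-CoV-2, who may have dose 2 after recovery. The remaining one-dose members of that arm are selected by other post-randomisation events. Leaving at booster is a further post-baseline selection.
- *Prior infection.* Section 6.4 lets recovered placebo recipients take the single dose and recovered active-arm participants take the second. Prior infection can thus enter both cohorts, and the sign of any net difference is unknown.

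**Step 3. Does a listed objective use the randomisation?** The active-phase objectives concern symptomatic, severe/critical and medically attended COVID-19, deaths, severity, immunogenicity, correlates, and duration after booster. The passive-phase objectives concern COVID-19 adverse events, immunogenicity and correlates. None compares newly enrolled participants by assigned schedule. The one efficacy contrast named in the Synopsis for this phase is boosted versus not boosted on the same primary regimen.

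**Step 4. Would the randomised contrast be informative?** The protocol does not give the number newly enrolled. As an illustration only, assume N per arm from 250 to 2,500, one year of follow-up, a one-dose rate r of 1% or 4% (borrowed from the sizing assumption for moderate to severe/critical disease), and a two- to one-dose rate ratio RR of 0.5 or 0.7.

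Events: d = N × r × (1 + RR). Power at two-sided 5%: Φ(|ln RR| × √(d/4) − 1.96).

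- N = 250, r = 1%, RR = 0.7: d = 4.25, power about 6%.
- N = 1,000, r = 4%, RR = 0.7: d = 68, power about 31%.
- N = 2,500, r = 4%, RR = 0.5: d = 150, power about 99%.

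Precision could be anything from negligible to good, so the illustration settles nothing about its value for efficacy.

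**The case against.** The strongest reply is that nothing is lost. The Synopsis leaves the open-label populations to the SAP, the analyses are descriptive, adjustment for confounding (including the spread of variants over place and time) will be explored, and Section 2.1 admits the loss of randomisation. Sections 8.1.4 and 9.7, listed in the contents, and the SAP were not in the text available here.

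Much of this stands, and it rules out several stronger readings:

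- *A reader might infer that the randomised comparison is discarded.* No text drops the assignment or forbids an analysis by it.
- *A reader might call it the only randomised schedule comparison.* Original Group 1 versus Group 2 (two doses versus placebo, then a delayed single dose) also rests on randomisation, though with different timing and incomplete cross-over.
- *A reader might say that the stated purpose of the 1:1 randomisation goes unserved.* The rationale sentence refers to following all participants, and its mention of different starting times fits the cross-overs.
- *A reader might argue that infection between doses fills the one-dose cohort with immune participants and flatters one dose.* The exception in Section 6.4 undercuts that route. Any percentage put on it would rest on an assumed infected share and an assumed reinfection rate.

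What the reply does not answer is that the cohorts and objectives are fixed in the protocol itself, and they do not deliver the comparison announced in Section 2.1. The reason given for the loss of randomisation, incomplete cross-over from placebo, does not apply to the newly enrolled. Knowledge of the number of doses does apply to them and would remain a limitation.

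**Conclusion.** The point holds as an inconsistency between the announced schedule comparison and the cohorts and objectives provided for it. Any one- versus two-dose contrast between the cohorts as defined is non-randomised and confounded by calendar time and variant, time since dose, and selection into one dose. Prior infection may add to this in either direction. The Amendment 4 participants are the only ones randomised to one versus two active doses both starting on Day 1, and no listed objective compares them that way.

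No size can be put on the bias from the documents. The conclusion rests on the wording of the cohort definitions and objectives, and on the natural reading that newly enrolled one-dose participants sit in the one-dose cohort. It affects descriptive open-label results and leaves the double-blind primary analysis untouched. It is a worthwhile improvement to the analysis and does not show that the SAP omits the comparison.

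**What to change.** 1. Flag every cohort member by origin: newly randomised under Amendment 4, placebo cross-over, or original active arm (with or without dose 2).
2. Add a descriptive comparison of one versus two doses among the newly enrolled, by assigned schedule, for COVID-19 incidence and whatever immunogenicity data exist for them.
3. State how booster and outside vaccination are handled (for example, censoring), and use a common start of follow-up. The open-label endpoints count from 28 days after the last vaccination, which is Day 29 on one schedule (1 + 28) and Day 85 on the other (57 + 28).
4. Keep the pooled as-received cohorts as supportive, with a note that contrasts between them are not randomised.

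If the comparison is judged not worth making, amend the statement in Section 2.1 (Study Rationale) instead.

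The cost is one derived flag, since assignment is held in IWRS, and a few tables. The drawback is that precision may be low and cannot be judged until the number newly enrolled is stated.

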2.2 Open-label Passive Follow-up Phase

With the implementation of Protocol Amendment 7, the active follow-up of suspected COVID-19 episodes is replaced by a passive follow-up. Participants will enter this phase on the day of consenting to Amendment 7 (or with the stop of the eCOA at each study site, whichever comes first) until end of study.

In the passive follow-up phase, the same cohorts as from the open-label active phase are included, and all data will be descriptively presented by cohort depending on the vaccination schedule received during the follow-up phase. Since COVID-19 reporting changed from an active approach to a passive approach, the evaluations will be limited. Efficacy evaluations may be performed if feasible and will be described in the SAP as applicable.

Passive follow-up of COVID-19 consists of recording of new COVID-19 episodes as SAEs, AEs, or MAAEs. The information of these AEs is collected during the scheduled phone calls with the participants.

The list of objectives and endpoints of the passive follow-up phase are:

Objectives	Endpoints
Secondary	
The secondary safety objective of the double-blind phase (see secondary double-blind objectives)	
 The secondary safety endpoint of the double-blind phase (see secondary double-blind endpoints) during the entire follow-up period
Exploratory	
To evaluate COVID-19 ^a in terms of (S)AEs MAAEs, hospitalizations and fatal AE linked to COVID-19 in the different study cohorts	
 SAEs and AEs linked to COVID-19 MAAEs linked to COVID-19 AEs linked to COVID-19 that require hospitalization Fatal AEs linked to COVID-19^b
In a subset of participants, to evaluate the immunogenicity of Ad26.COV2.S in the different study cohorts	
 Analysis of antibodies binding to the SARS-CoV-2 S protein by ELISA Analysis of SARS-CoV-2 neutralizing antibody titers as measured by psVNA and/or wtVNA
If feasible, to estimate a correlate of immunity (correlate of risk) in relation to the primary endpoint of the main study and serious disease, hospitalization, and death based on available immune responses in the different study cohorts	
 Analysis of binding antibody titer measured by S-ELISA and/or MSD assay, as available, for participants having COVID-19 compared to non-infected participants and/or MSD assay Analysis of SARS-CoV-2 neutralizing antibody titers measured by psVNA or wtVNA, as available, for participants having COVID-19 compared to non-infected participants

^a Refer to Section 8.3 for the safety follow-up and COVID-19 reporting requirements as of Protocol Amendment 7.

^b Fatal AEs linked to COVID-19 as determined by the Clinical Severity Adjudication Committee

Case Definitions

The Clinical Severity Adjudication Committee will be utilized for adjudication of the severity of COVID-19 cases taking into account all available relevant information at the time of adjudication. As of Amendment 7, the Clinical Severity Adjudication Committee may review all cases based on available data from the passive follow-up (eg, limited to COVID-19 AE/SAE data, CIOMS forms, local laboratory results). Details will be provided in the revised charter of the Clinical Severity Adjudication Committee. Readjudication will occur if new information becomes available. The last adjudication for a given case will determine the status of the case for analysis. The Clinical Severity Adjudication Committee's decision will be considered the definitive classification of the case. The role of the Committee and adjudication process will be provided in the committee's charter and more details regarding the impact on the analysis will be provided in the SAP. The case review including severity assessments after implementation of Protocol Amendment 7 may change and will be reflected in the charter of the committee.

The criteria for suspected COVID-19 are described in the body of the protocol. As several of the prespecified criteria for suspected COVID-19 overlap with vaccine-related reactogenicity, investigators' clinical judgement is required to exclude vaccine-related events when assessing suspected COVID-19.

Case Definition for Moderate to Severe/Critical COVID-19

For the primary endpoint (see above), all moderate and severe/critical COVID-19 cases will be considered.

Case Definition for Moderate COVID-19

- A SARS-CoV-2 positive RT-PCR or molecular test result from any available respiratory tract sample (eg, nasal swab sample, sputum sample, throat swab sample, saliva sample) or other sample

AND at any time during the course of observation^a:

Any 1 of the following new or worsening signs or symptoms:

- Respiratory rate ≥ 20 breaths/minute
- Abnormal saturation of oxygen (SpO_2) but still $>93\%$ on room air at sea level*
- Clinical or radiologic evidence of pneumonia
- Radiologic evidence of deep vein thrombosis (DVT)
- Shortness of breath or difficulty breathing

Any 2 of the following new or worsening signs or symptoms:

- Fever ($\geq 38.0^{\circ}\text{C}$ or $\geq 100.4^{\circ}\text{F}$)
- Heart rate ≥ 90 beats/minute
- Shaking chills or rigors
- Sore throat
- Cough
- Malaise as evidenced by 1 or more of the following**:
 - Loss of appetite
 - Generally unwell
 - Fatigue
 - Physical weakness
- Headache
- Muscle pain (myalgia)
- Gastrointestinal symptoms (diarrhea, vomiting, nausea, abdominal pain)**
- New or changing olfactory or taste disorders
- Red or bruised looking feet or toes

OR

* SpO_2 criteria will be adjusted according to altitude per the investigator judgement.

** Having 2 or more elements of a symptom (eg, vomiting and diarrhea or fatigue and loss of appetite) is counted only as 1 symptom for the case definition. To meet the case definition, a participant would need to have at least 2 different symptoms.

Case Definition for Severe/Critical COVID-19

- A SARS-CoV-2 positive RT-PCR or molecular test result from any available respiratory tract sample (eg, nasal swab sample, sputum sample, throat swab sample, saliva sample) or other sample

AND any 1 of the following at any time during the course of observation^a:

- Clinical signs at rest indicative of severe systemic illness (respiratory rate ≥ 30 breaths/minute, heart rate ≥ 125 beats/minute, oxygen saturation (SpO_2) $\leq 93\%$ on room air at sea level*, or partial pressure of oxygen/fraction of inspired oxygen ($\text{PaO}_2/\text{FiO}_2$) < 300 mmHg)

* SpO_2 criteria will be adjusted according to altitude per the investigator judgement.

- Respiratory failure (defined as needing high-flow oxygen, non-invasive ventilation, mechanical ventilation, or extracorporeal membrane oxygenation [ECMO])

^a Until Amendment 7, participants will be asked to undertake the COVID-19 procedures until 14 days after symptom onset (COVID-19 Day 15) or until **resolution of the COVID-19 episode**, whichever comes last (see Section 8.1.2).

- Evidence of shock (defined as systolic blood pressure <90 mmHg, diastolic blood pressure <60 mmHg, or requiring vasopressors)
- Significant acute renal, hepatic, or neurologic dysfunction
- Admission to the ICU
- Death

Case Definition for Mild COVID-19

- A SARS-CoV-2 positive RT-PCR or molecular test result from any available respiratory tract sample (eg, nasal swab sample, sputum sample, throat swab sample, saliva sample) or other sample

AND at any time during the course of observation^a:

- One of the following symptoms: fever ($\geq 38.0^{\circ}\text{C}$ or $\geq 100.4^{\circ}\text{F}$), sore throat, malaise (loss of appetite, generally unwell, fatigue, physical weakness), headache, muscle pain (myalgia), gastrointestinal symptoms, cough, chest congestion, runny nose, wheezing, skin rash, eye irritation or discharge, chills, new or changing olfactory or taste disorders, red or bruised looking feet or toes, or shaking chills or rigors.

A case is considered mild when it meets the above case definition but not the moderate to severe/critical definition.

US FDA Harmonized Case Definition for COVID-19

If a participant presents with symptoms as those listed by the US FDA harmonized case definition (see appendix to the protocol), the investigator (or designated medically trained clinician) should assess if these are suggestive of COVID-19:

- A SARS-CoV-2 positive RT-PCR or molecular test result from any available respiratory tract sample (eg, nasal swab sample, sputum sample, throat swab sample, saliva sample) or other sample; **AND**
- COVID-19 symptoms consistent with those defined by the US FDA harmonized case definition at the time of finalization of this protocol: fever or chills, cough, shortness of breath or difficulty breathing, fatigue, muscle or body aches, headache, new loss of taste or smell, sore throat, congestion or runny nose, nausea or vomiting, diarrhea.

Case Definition for Asymptomatic or Undetected COVID-19

If a participant does not fulfil the criteria for suspected COVID-19 based on signs and symptoms, which would classify them as mild or moderate to severe/critical by the protocol definitions mentioned above,

AND

- has a SARS-CoV-2 positive RT-PCR or molecular test result from any available respiratory tract sample (eg, nasal swab sample, sputum sample, throat swab sample, saliva sample) or other sample

OR

- develops a positive serology (non-S protein) test

Then, the participant will be considered to have experienced asymptomatic or undetected COVID-19.

^a Until Amendment 7, participants will be asked to undertake the COVID-19 procedures until 14 days after symptom onset (COVID-19 Day 15) or until **resolution of the COVID-19 episode**, whichever comes last (see Section 8.1.2).

For any case definition to be considered for classification of COVID-19 there needs to be at least one SARS-CoV-2 positive RT-PCR or molecular test result from any available respiratory tract sample (eg, nasal swab sample, sputum sample, throat swab sample, saliva sample) that is confirmed by the central laboratory. It is possible that not all samples can be confirmed at the time of the analysis. Hence a sensitivity analysis may be performed using all RT-PCR or molecular test result, regardless of the confirmation by the central laboratory.

As of Amendment 7, severity assessment by the CSAC may still be performed and will be based on the data collected through the passive follow-up (eg, hospitalization reported in the context of SAEs). The scope of the severity review may change and will be described in the charter.

OVERALL DESIGN

This is a multicenter, randomized, double-blind, placebo-controlled, Phase 3, pivotal efficacy and safety study in adults ≥ 18 years of age. The efficacy, safety, and immunogenicity of Ad26.COV2.S will be evaluated in participants living in, or going to, locations with high risk for acquisition of SARS-CoV-2 infection after administration of 2 doses of study vaccine.

Initial immunogenicity and safety data (28 days post dose 1 data from Cohort 1a and available data from Cohort 3) from study VAC31518COV1001 have demonstrated that a single dose of Ad26.COV2.S at 5×10^{10} vp and 1×10^{11} vp induces an immune response that meets prespecified minimum criteria and has an acceptable safety profile. The sponsor has therefore decided to proceed with an Ad26.COV2.S dose level of 5×10^{10} vp in its Phase 3 studies. Even though a single-dose regimen in study VAC31518COV1001 showed good immunogenicity that may already protect against COVID-19, data from other vaccines using the Ad26 platform suggest that a second vaccination may potentially result in an increased and more durable immune response, providing justification for the evaluation of a 2-dose regimen in this study. The single dose regimen will be further evaluated in study VAC31518COV3001.

Participants will be randomized in parallel in a 1:1 ratio in the double-blind phase of the study to receive Ad26.COV2.S or placebo intramuscularly (IM) as shown in the table below. Ad26.COV2.S will be administered at a dose level of 5×10^{10} vp.

Following Ad26.COV2.S EUA in the US, all participants from countries where Protocol Amendment 4 is approved by both the Health Authority and the IEC/IRB will be unblinded at the on-site or remote unblinding visit. The unblinding of all participants and vaccination of placebo recipients may be conducted as soon as reasonably practicable and preferably no later than 2 months after local approvals of Protocol Amendment 5 have been received. Investigators will be encouraged to follow local health authority guidelines on prioritization of immunization. If a scheduled study visit is planned within 2 months of the local approval of Protocol Amendment 5, the unblinding visit may be combined with this planned study visit. Every effort should be made to combine the unblinding visit with a scheduled visit; otherwise, it must be done as an unscheduled visit. In the event that the unblinding takes place at a scheduled visit, procedures that would be duplicated should be done only once.

Participants from the placebo arm enrolled during the double-blind phase will be offered to receive a single dose of Ad26.COV2.S vaccine (open-label vaccination), unless they met certain vaccination discontinuation rules during the double-blind phase of the study.

Participants from the Ad26.COV2.S arm enrolled during the double-blind phase will continue in the same arm to receive their second dose, if applicable.

Newly enrolled participants in the open-label phase under Amendment 4 will be randomized in a 1:1 ratio to receive either 1 dose or 2 doses of Ad26.COV2.S vaccine. After the study pause, the unblinding visit was scheduled as soon as reasonably practicable and preferably no later than 2 months following local approvals of Protocol Amendment 5 were received.

As of implementation of Protocol Amendment 6, all ongoing eligible participants who received only a single vaccination with Ad26.COV2.S in the study will be offered a single booster dose of Ad26.COV2.S vaccine (5×10^{10} vp) (see table below). Participants who already received 2 vaccinations with Ad26.COV2.S at the 5×10^{10} vp dose level or any COVID-19 vaccinations outside of the study (including the Janssen vaccine) at the time of local approval of Protocol Amendment 6 are not eligible to receive a booster vaccination with Ad26.COV2.S. The booster vaccination will be administered in the open-label phase of the study, preferably within 6 to 12 months after the participant's first Ad26.COV2.S vaccination in the study. If this is not possible, the booster vaccination should not occur earlier than 3 months after the participant's first Ad26.COV2.S vaccination. The Booster Vaccination Visit should preferably coincide with the participant's next scheduled visit (ie, Visit 7 or Visit 8 for the majority of participants) from the original Schedule of Activities (SoA). If not operationally feasible to coincide with an existing visit, an unscheduled visit may be planned. After the booster vaccination visit, participants will continue procedures and visits as in the original SoA. All participants (whether they consent to the booster vaccination or not) will be encouraged to remain in the study and will be monitored for safety, immunogenicity, and efficacy according to their original schedule.

With Amendment 7, active follow-up of suspected COVID-19 will be replaced by passive surveillance (ie, follow-up phone call visits by the site instead of on-site study visits to document new COVID-19 events as [S]AEs and MAAEs) and to record concomitant therapies associated with COVID-19, if available. During these calls, the protocol required safety information (eg, [S]AEs, AESIs, MAAEs 6 months after the last vaccination) are also collected.

Vaccination Schedule VAC31518COV3009 – Double-blind Phase

Group	N	Day 1	Day 57
1	Approx. 15,000	Ad26.COV2.S (5×10^{10} vp)	Ad26.COV2.S (5×10^{10} vp)
2	Approx. 15,000	Placebo	Placebo

N number of participants; vp virus particles.

Note: It is intended that a minimum of approximately 30% of recruited participants will be ≥ 60 years of age and approximately 20% of recruited participants will be ≥ 18 to < 40 years of age.

Vaccination Schedule VAC31518COV3009 – Open-label Phase

Group	N*	Day 1	Day 57	Unscheduled Unblinding visit**/Day 1 for newly enrolled participants***	Booster Vaccination Preferably Vac 1 + 6-12 months Minimally Vac 1 + 3 months*****
1	Approx. 15,000	Ad26.COV2.S (5×10^{10} vp)	Ad26.COV2.S (5×10^{10} vp)		Ad26.COV2.S
2	Approx. 15,000	Placebo***	Placebo****	Ad26.COV2.S (5×10^{10} vp)	(5×10^{10} vp)

N number of participants; vp virus particles.

Note: It is intended that a minimum of approximately 30% of recruited participants will be ≥ 60 years of age and approximately 20% of recruited participants will be ≥ 18 to < 40 years of age.

* It is possible that there might be over enrollment of participants in this study.

** All participants will be unblinded (informed whether they received placebo or Ad26.COV2.S) at the on site or remote unblinding visit following EUA in the US and approval of Protocol Amendment 4 by the local Health Authority and IEC/IRB, and the study will continue as an open label study. Participants who were in the placebo arm will be offered to receive a single dose of Ad26.COV2.S 5×10^{10} vp. After the study pause, the unblinding visit should be scheduled as soon as reasonably practicable and preferably no later than 2 months following local approvals of Protocol Amendment 5 have been received. The unblinding visit may be combined with the next planned study visit, if appropriate.

*** Newly enrolled participants will be randomized to Group 1 (to receive two doses of Ad26.COV2.S) or to Group 2 (to receive one dose of Ad26.COV2.S on Day 1 instead of 2 doses of placebo (there will be no administration of placebo on Day 57).

**** Vaccination at Day 57 is not applicable for participants who were unblinded after the placebo vaccination at Day 1 and prior to receiving the second placebo vaccination.

*****Following implementation of Protocol Amendment 6, all ongoing eligible participants who received only 1 Ad26.COV2.S vaccination in the study will be offered 1 Ad26.COV2.S booster vaccination. Participants who already received 2 vaccinations with Ad26.COV2.S at the 5×10^{10} vp dose level or any COVID 19 vaccinations outside of the study (including the Janssen

vaccine) at the time of local approval of Protocol Amendment 6 are not eligible to receive a booster vaccination with Ad26.COV2.S.

A staggered enrollment strategy will be used in the double-blind phase:

- Stage 1: Initially, approximately 1,000 participants without comorbidities that are associated with increased risk of progression to severe COVID-19 (including approximately 500 Ad26.COV2.S recipients and approximately 500 placebo recipients) will be enrolled.
- Stage 2: After a vaccination pause in Stage 1 to allow the Independent Data Monitoring Committee (IDMC) to examine Day 3 safety data (ie, from Day 1 to Day 3; including safety data from the ongoing studies), if no safety concerns are identified enrollment will proceed, expanding enrollment to include participants with and without comorbidities that are associated with increased risk of progression to severe COVID-19 in 2 age-dependent subgroups (≥ 18 years to < 60 years of age and ≥ 60 years of age).

Comorbidities (or risk factors) that are or might be associated with an increased risk of progression to severe COVID-19^a include: moderate-to-severe asthma; chronic lung diseases such as chronic obstructive pulmonary disease (COPD) (including emphysema and chronic bronchitis), idiopathic pulmonary fibrosis and cystic fibrosis; diabetes (including type 1 or type 2); serious heart conditions, including heart failure, coronary artery disease, congenital heart disease, cardiomyopathies, and pulmonary hypertension; moderate to severe high blood pressure; obesity (body mass index [BMI] ≥ 30 kg/m²); chronic liver disease, including cirrhosis; sickle cell disease; thalassemia; cerebrovascular disease; neurologic conditions (dementia); end stage renal disease; organ transplantation; cancer; human immunodeficiency virus (HIV) infection and other immunodeficiencies; hepatitis B infection; sleep apnea; and participants who live in nursing homes or long-term care facilities.

